Statistical Analysis Plan for Clinical Study I4T-MC-JVCY

A Multicenter, Randomized, Double-Blind Study of Erlotinib in Combination with Ramucirumab or Placebo in Previously Untreated Patients with *EGFR* Mutation-Positive Metastatic Non-Small Cell Lung Cancer

NCT02411448

Approval Date: 13-Dec-2018

1. Statistical Analysis Plan for Clinical Study: I4T-MC-JVCY: A Multicenter, Randomized, Double-Blind Study of Erlotinib in Combination with Ramucirumab or Placebo in Previously Untreated Patients with *EGFR*Mutation-Positive Metastatic Non-Small Cell Lung Cancer

Confidential Information

The information contained in this Statistical Analysis Plan (SAP) is confidential and the information contained within it may not be reproduced or otherwise disseminated without the approval of Eli Lilly and Company or its subsidiaries. This document and its associated attachments or appendices are subject to United States Freedom of Information Act Exemption 4.

Ramucirumab (LY3009806) Non-Small Cell Lung Cancer

This is a multicenter, randomized, double-blind, Phase 3 study that will compare the efficacy and safety of treatment with erlotin b (150 mg daily) and ramucirumab (10 mg/kg every 2 weeks) versus erlotinib (150 mg daily) and placebo (10 mg/kg every 2 weeks) in previously untreated patients with *EGFR* mutation-positive metastatic NSCLC. Treatment will continue until disease progression, unacceptable toxicity, or another permitted reason for study discontinuation. This Phase 3 part (Part B) is preceded by a Phase 1b part (Part A) to assess the safety and tolerability for the combination of ramucirumab plus erlotin b. In addition, Part C, an open-label, 2-period, single-arm, exploratory cohort is added to the main protocol.

Eli Lilly and Company Indianapolis, Indiana USA 46285 Protocol I4T-MC-JVCY Phase 1b/3

Statistical Analysis Plan (SAP) Version 3 electronically signed and approved by Lilly on date provided below.

SAP Version 2 electronically signed and approved by Lilly: 31 May 2018 SAP Version 1 electronically signed and approved by Lilly: 17 April 2015

Approval Date: 13-Dec-2018 GMT

2. Table of Contents

Section	Page
1. Statistical Analysis Plan for Clinical Study: I4T-MC-JVCY: A Multicenter, Randomized, Double-Blind Study of Erlotinib in Combination with Ramucirumab or Placebo in Previously Untreated Patients with EGFR Mutation-Positive Metastatic Non-Small Cell Lung Cancer	1
2. Table of Contents	2
3. Revision History	5
4. Study Objectives	7

5.18. CCI	
5.19. Clinical Trial Registry Analyses	39
6. Unblinding Plan	40
6.1. Site Level Unblinding	40
6.2. Sponsor/Trial Level Unblinding	41
7. References	42

Table of Contents

Table		Page
Table JVCY.5.1.	Rules for Determining Date of Progression or Censor for Progression-Free Survival	13
Table JVCY.5.2.	Ramucirumab/Placebo Dose Reduction Schedule	16
Table JVCY.5.3.	Erlotinib Reduction Schedule	16

3. Revision History

Statistical analysis plan (SAP) Version 1 was approved prior to the first patient visit.

SAP Version 2 was approved 31 May 2018, prior to the primary PFS analysis. The overall changes incorporated in SAP Version 2 were as follows:

- 1) The number of progression-free survival (PFS) events required to perform the primary analysis was updated from approximately 320 events to approximately 270 events.
- 2) Removed the interim PFS efficacy analysis that was to occur at approximately 224 PFS events.
- 3) Exploratory objectives and its analyses plan for Part C were added.
- 4) Determination of sample size for Part C was described.
- 5) Analysis populations for Part C were defined.
- 6) Description of interim analysis related to Part C was added.
- 7) Updated the rules for determining date of progression or censor for the PFS primary analysis.
- 8) Updated the PFS sensitivity analyses.
- 9) Added Part B Per-Protocol population definition.
- 10) Clearly stated that Interactive Web Response System (IWRS) stratification values will be used for the primary PFS analysis.
- 11) Changed the terminology of "protocol violation" to "protocol deviation".
- 12) Added additional age groups.
- 13) Updated selected concomitant medications.
- 14) Added progression-free survival 2 (PFS2) and overall survival (OS) analyses for patients who receive osimertinib after disease progression vs. those who do not
- 15) Added the following analyses:
 - a. time-to-brain metastases analysis.
 - b. exposure analyses by months.
 - c. summary of treatment-emergent adverse events (TEAEs) by narrowscope standardized Medical Dictionary for Regulatory Activities (MedDRA) queries (SMQs) and preferred term (PT).
- 16) Other minor changes, including editorial changes.

SAP Version 3 was approved prior to the primary PFS analysis. The overall changes incorporated in SAP Version 3 were as follows:

- 1) Revised the protocol deviation section.
- 2) Clarified that Part C was conducted in the East Asian region, including Japan.
- 3) Clarified which analyses will be conducted for Parts A, B, or C.
- 4) Added liver metastases as a subgroup analysis
- 5) Added dose modification definitions
- 6) Defined time to diagnosis of CNS metastases
- 7) Defined more exposure parameters for each study part
- 8) Added a sensitivity analysis for primary PFS without censoring for either missed visits or new anticancer therapy
- 9) Defined immunogenicity-related variables
- 10) Added 75 age subgroup analyses per EU requirement
- 11) Added a sensitivity analysis of ORR/DCR/DOR based on independent assessment
- 12) Other minor changes, including editorial changes

4. Study Objectives

The study is divided into 3 parts. Part A is the Phase 1b single arm safety lead-in portion of the trial and Part B is the randomized double blinded Phase 3 portion of the trial. Part C is an open-label, 2-period, single-arm, exploratory cohort that was added to the main protocol (I4T-MC-JVCY [JVCY]) and is only applicable to sites in the East Asian region, including Japan (see protocol addendum 9.2, approved on 23 May 2018).

4.1. Primary Objective

The objective(s) for each part are as follows:

Part A: The objective of Part A is to assess the safety and tolerability of ramucirumab when administered in combination with erlotinib as therapy in previously untreated patients with epidermal growth factor receptor (*EGFR*) mutation-positive metastatic non-small cell lung cancer (NSCLC).

Part B: The primary objective of Part B is to compare the progression-free survival (PFS) of ramucirumab administered in combination with erlotinib versus placebo in combination with erlotinib in previously untreated patients with *EGFR* mutation-positive metastatic NSCLC.

Part C: All objectives for Part C are exploratory. Please see Section 4.3.

4.2. Secondary Objectives

Part A: There is no secondary objective planned for Part A.

Part B: Secondary objectives of Part B are to compare ramucirumab administered in combination with erlotinib versus placebo administered in combination with erlotinib for:

- safety and toxicity profile
- overall survival (OS)
- objective response rate (ORR) (complete response [CR] + partial response [PR])
- disease control rate (DCR) (CR + PR + stable disease [SD])
- duration of response (DOR)
- pharmacokinetics (PK) and immunogenicity of ramucirumab
- patient-reported outcomes (PROs; using Lung Cancer Symptom Scale [LCSS] and EuroQol 5-dimension, 5-level questionnaire [EQ-5D-5L])
- Drug-Drug Interaction (DDI) substudy to assess the pharmacokinetics of erlotinib with and without ramucirumab

4.3. Exploratory Objectives

The exploratory objectives of both Parts B and C are to:

- assess the association between biomarkers and clinical outcome.
- assess progression-free survival 2 (PFS2).
- assess time to deterioration (TtD) in Eastern Cooperative Oncology Group (ECOG) performance status (PS)

- assess time to diagnosis of CNS metastases.
- progression-free survival 2 (PFS2) and overall survival (OS) analyses for patients who receive osimertinib after disease progression vs. those who do not.

The additional exploratory objectives of Part C only are to:

- evaluate the efficacy (for example, 1-year PFS rate) and safety of ramucirumab when administered in combination with gefitinib in previously untreated patients with EGFR mutation-positive metastatic NSCLC, in the East-Asian region including Japan
- evaluate the efficacy and safety of ramucirumab when administered in combination with osimertinib in patients with T790M-positive metastatic NSCLC and who have progressed on ramucirumab plus gefitinib in this study, in the East-Asian region including Japan
- assess pharmacokinetics (PK) and immunogenicity of ramucirumab
- assess patient-reported outcomes (using Lung Cancer Symptom Scale and EuroQol 5 dimension, 5-level questionnaire)

5. A Priori Statistical Methods

5.1. Determination of Sample Size

5.1.1. Part A

At least 12 (6 from Japan and 6 from North America and/or Europe) previously untreated patients with *EGFR* mutation-positive metastatic NSCLC will be enrolled and treated with ramucirumab plus erlotinib.

5.1.2. Part B

The study will enroll approximately 450 patients in 1:1 randomization (that is, approximately 225 patients will be randomly assigned to each treatment arm). The primary PFS analysis will be performed after approximately 270 PFS (approximately 40% censoring rate) events.

An interim futility analysis was conducted at 114 investigator-assessed PFS events (data cutoff date 16 October 2017), and the IDMC recommended the trial continue without modification. A nominal 1-sided alpha <0.00001 was spent in order to maintain type-I error. Assuming an HR of 0.71, this sample size yields at least 80% statistical power to detect superiority of the ramucirumab plus erlotinib arm over the placebo plus erlotinib arm, with the use of a 1-sided log-rank test and a type I error of 0.02499. If the true median PFS for the placebo plus erlotinib arm is 11 months, then the HR of 0.71 amounts to an approximate 4.5-month improvement in median PFS for the ramucirumab plus erlotinib arm under an additional assumption of exponential survival distribution.

Sample size calculation is carried out in EAST Version 6.4 (1994-2016).

5.1.3. Part C

Approximately 80 previously untreated patients with EGFR mutation-positive metastatic NSCLC will be enrolled from East Asia, including Japan, and treated with ramucirumab plus gefitinib in Period 1.

Ichihara et al. (2015) reported a 1-year PFS rate of 56.7% (95% CI: 39.9, 70.5) for bevacizumab plus gefitinib in patients with EGFR mutation-positive metastatic NSCLC. Given an expected 1-year PFS rate of 55% for ramucirumab plus gefitinib, when 80 patients are enrolled, asymptotic 95% confidence interval half-width for expected 1-year PFS rate with normal approximation is approximately 11%.

5.1.4. Drug-Drug Interaction Substudy

Pharmacokinetic parameters of erlotinib will be compared between the ramucirumab plus erlotinib arm and the placebo plus erlotinib arm. Around 15 patients from each treatment arm (approximately 30 patients in total) were deemed sufficient for the initial analysis of PK. Based on an intra-subject coefficient of variation in area under the concentration-time curve (AUC) of 16% obtained from erlotinib PK analyses (Hamilton et al. 2014) and assuming 60% of the total variability (26.7%) contributed by the within-patient variability, a sample size of 15 patients in

each treatment arm will provide a precision of approximately 0.191 in the log scale for the ratio of geometric means of AUC. That is, there is a 90% probability that the half-width of the 90% confidence interval (CI) will be within 0.191 for the estimated ratio of geometric means of AUC of erlotinib in the presence and absence of ramucirumab.

5.2. General Considerations

Part A: The analyses for Part A will be descriptive. Data analyses will be provided separately for study patients in the 2 geographic areas: 1) Japan, 2) European Union (EU) and United States, and 3) total. The list of analyses conducted for the Assessment Committee (AC) review is included in the AC charter.

Part B: All tests of treatment effects will be conducted at a two-sided alpha level of 0.05, and all CIs will be given at a two-sided 95% level, unless otherwise stated. Statistical analysis will be performed using SAS software (SAS, Version 9.2 or higher).

Part C: This part is only applicable to sites in the East-Asian region, including Japan. The analyses for Part C will be descriptive and conducted separately from Parts A and B. Results of Part C will be included in a separate addendum to the clinical study report (CSR) for Parts A and B. Safety data of Part C will be summarized by each period. Patients who do not enter Period 2 will not be included in summary safety analyses for Period 2.

This document describes the statistical analyses planned prior to final treatment assignment unblinding of the aggregate database. Any change to the data analysis methods described in the protocol will require an amendment ONLY if it changes a principal feature of the protocol. Before unblinding of the aggregate database, minor modifications or clarifications to the data analysis methods may be described and justified in this document. Any other change to the data analysis methods described in the protocol and the justification for making the change will be described in the CSR. The assumptions for each statistical method may be evaluated. If there is violation of assumptions, alternative statistical methods may be used. Additional exploratory analyses of the data will be conducted as deemed appropriate. The SAP will not be updated to reflect post-hoc analyses conducted after unblinding. These will be described in the study report as appropriate.

Statistical analysis of this study will be the responsibility of Lilly or its designee. The study PK scientist will be responsible for designing, conducting, and interpreting the PK analysis and delivering PK parameters. The interpretation of final study results will be the responsibility of the clinical research physician (CRP) and the study statistician. These individuals will also be responsible for the appropriate conduct of an internal review process for both the CSR and any study-related material to be authorized for publication by Lilly.

The following general terms will be used globally in the SAP:

- Unless otherwise specified, **summary statistics** stand for n, mean, standard deviation, median, Q3-Q1, minimum, and maximum for continuous variables; and frequency and percentage for categorical variables.
- Study period

- O Dose-limiting toxicity (DLT) assessment period for Part A: for individual patient assessment, period begins on the day of the first study drug dose and ends on the day when the patient:
 - o completed 2 cycles of treatment, or
 - o discontinued from study treatment or study participation before completing 2 cycles due to a DLT.

Note. Two cycles are considered completed on the 14th day from the second dose of ramucirumab.

- o **Study treatment period** begins at the first dose of study treatment and ends when the patient and the investigator agree that the patient will no longer continue any study treatment. The date of this agreement is to be reported on the electronic case report form (eCRF) as the Date of Discontinuation from all study treatment.
- o **30-day short-term follow-up period** begins the day after the patient and the investigator agree that the patient will no longer continue any study treatment and lasts approximately 30 days (± 3 days).
- O Long-term follow-up period begins the day after short-term follow-up is completed and continues every 6 weeks (± 7 days) until progressive disease (PD), thereafter every 3 months (± 7 days) until the patient's death, withdrawal of consent to participate or overall study completion, whichever occurs first.

5.3. Definitions of Analysis Variables

Definitions of efficacy, safety, and patient-reported outcome (PRO) analysis variables are listed in Section 5.3.1, Section 5.3.2, and Section 5.3.3, respectively. Other variables are listed below alphabetically.

- **Age (years)**: (Informed Consent Date Date of Birth + 1)/365.25. **Note.** Average days in a year = 365.25, reflecting the Julian Calendar of 3 years with 365 days each and one leap year of 366 days. Birth month and day are imputed to be 01 July because only birth year is collected through the eCRF.
- **Baseline measurement** is the last non-missing measurement prior to first dose for safety analyses, and the last non-missing measurement prior to randomization for demographic and efficacy analyses.
- **Duration** is calculated as:
 - o Duration (days): (End Date Start Date + 1)
 - o Duration (weeks): (End Date Start Date + 1)/7
 - O Duration (months): (End Date Start Date + 1)/30.4375 **Note.** Days in months = (1/12)*average number of days in a year
 - o Duration (years): (End Date Start Date + 1)/365.25
- **Duration of disease** is defined as months from first diagnosis of cancer to randomization.

- **Smoking history (never/ever)** is defined as ever for patients who ≥100 cigarettes, cigars, or pipe-fulls in his/her lifetime by study entry and never otherwise.
- Study treatment day indicates the number of days the patient has been receiving study treatment. It is calculated as assessment date first dose date + 1 day if the assessment is done on or after the first dose day. If the assessment is done prior to the first dose day, study day will be calculated as assessment date first dose date. Date of first dose is defined as study Day 1.

5.3.1. Efficacy Analysis Variables

Definition of efficacy analysis variables are listed below in order of importance.

Progression-free survival (PFS) is defined as the time from the date of randomization until the date of radiographic documentation of progression (as defined by RECIST v. 1.1) or the date of death due to any cause, whichever is earlier. Table JVCY.5.1 lists rules for determining date of progression or censor for PFS. The censoring is taken in the following order:

- If a patient does not have a baseline disease assessment, then the PFS time will be censored at the randomization date, regardless of whether or not objective PD or death has been observed for the patient; otherwise,
- If a patient is not known to have died or have PD as of the data-inclusion cut-off date for the analysis, the PFS time will be censored at the date of last postbaseline adequate radiological tumor assessment, or at the date of randomization if the patient does not have any postbaseline adequate radiological assessment.

Note. If there are multiple dates associated with one radiological tumor assessment, the assessment date will be set to the first date when the overall response is PD and the last date otherwise. A radiological tumor assessment is considered adequate if its response is among CR, PR, SD, or PD.

PFS (day) = Date of progression or death / censor - Date of randomization + 1.

Table JVCY.5.1. Rules for Determining Date of Progression or Censor for Progression-Free Survival

Rule	Situation	Date of Progression or Censor	Outcome
1	No baseline tumor assessments	Date of Randomization	Censored
2	No postbaseline assessments and no death	Date of Randomization	Censored
3	No documented progression and no death (with a postbaseline tumor assessment)	Date of last adequate tumor assessment	Censored
4	Patient lost to follow-up (or withdrew consent from study participation) before documented progression or death	Date of last adequate tumor assessment	Censored
5	Documented progression	Date of documented progression	Progressed
		If a tumor assessment was done on multiple days, use the earliest date for that visit.	
6	Death without documented progression	Date of death Progresse	
7	Documented progression or death after missing ≥2 consecutive postbaseline tumor assessments	Date of last adequate tumor assessment before missed assessments or date of randomization, whichever is later	
8	New anticancer treatment started and no tumor progression or death within 14 days	Date of adequate tumor assessment prior to start of new anticancer treatment +14 days or date of randomization, whichever is later	Censored

Note: PFS and associated outcome is determined by the earliest of the dates above, if more than 1 situation applies.

Overall survival (OS) is defined as time from the date of randomization to the date of death from any cause. For each patient who is not known to have died as of the data-inclusion cut-off date for a particular analysis, OS will be censored for that analysis at the last date the patient was known to be alive (on or before the data-inclusion cut off date). Contacts considered in the determination of last date include adverse event [AE] date, lesion assessment date, visit date, and last known alive date.

Objective response rate (ORR) is defined as the proportion of randomized patients achieving a best overall response of PR or CR per RECIST v.1.1. Patients who do not have any postbaseline tumor response assessments for any reason are considered non-responders and are included in the denominator when calculating the response rate.

Note. Tumor assessments performed after initiation of new anticancer treatment (systemic therapy) will be excluded from evaluating the best overall response and DCR.

Disease Control Rate (DCR) is defined as the proportion of randomized patients achieving a best overall response of complete response (CR), partial response (PR), or stable disease (SD) per Response Evaluation Criteria In Solid Tumors Version 1.1 (RECIST v.1.1). Patients who do not have any postbaseline tumor response assessments for any reason are considered non-responders and are included in the denominator when calculating the response rate. **Note.** Best overall response is the best response recorded from the start of treatment until disease progression, in the order of CR, PR, and SD. Refer to Attachment 7 of the protocol for definitions of CR, PR, and SD.

Duration of Response (DOR) is defined from the date of first documented CR or PR (responder) to the date of objective progression or the date of death due to any cause, whichever is earlier. If a responder is not known to have died or have objective progression, then the patient will be censored at the date of last evaluable tumor assessment.

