5.11.1. Primary Efficacy Analyses

The primary efficacy analysis will be performed in the Part B ITT population. For the primary comparison of investigator-assessed PFS between the 2 assigned study treatment arms, a stratified log-rank test at alpha level of 0.04998 (2-sided) will be performed to test the following statistical hypotheses about the PFS HR for ramucirumab plus erlotinib over placebo plus erlotinib:

 H_0 : PFS $HR \ge 1.00$

H_a: PRS HR < 1.00

The stratification will be the same as that used for randomization in the IWRS. An unstratified log-rank test will also be performed.

The following analyses of PFS will also be performed:

- Summary of PFS events (number and percentage), censoring rate, and reasons for censoring
- Kaplan-Meier survival curve (Kaplan and Meier 1958) by treatment arm will be provided.
- Restricted mean difference in PFS between the treatment arms and its 95% CI, while the
 restriction time is defined by the latest time where the standard error of the PFS estimates
 are ≤ 0.075 months.
- The Kaplan-Meier method will be used to estimate parameters (medians, quartiles, and percentages), difference of percentages and associated 95% CI and p-values for landmark analyses on each treatment group at 3 month intervals, based on a normal approximation. Patients who did not have the event at the corresponding time point will be considered right-censored observations.
- HR for treatment effect will be estimated using Cox proportional hazards (PH) model (Cox 1972) stratified identically to the primary log-rank test with assigned treatment as the only covariate, reported with 2-sided 95% CIs. All randomized patients, according to the ITT principle, will be included in the analysis of this endpoint. This Cox PH model will be referred to as the primary Cox PH model henceforth.

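### PFS Rule 1 censors a patient without a baseline scan at randomization even if the patient has died, and no prespecified sensitivity analysis counts that death

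*SAP*

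**What the plan says.** SAP Section 5.3.1 defines PFS as the time from randomization to radiographic progression "or the date of death due to any cause, whichever is earlier". It then lists censoring conditions to be applied in order. The first covers a patient with no baseline disease assessment, for whom "the PFS time will be censored at the randomization date, regardless of whether or not objective PD or death has been observed".

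Table JVCY.5.1 repeats this. Rule 1, "No baseline tumor assessments", gives the randomization date and the outcome censored, with no exception for death. Rule 2 is worded differently: "No postbaseline assessments and no death". Rule 6 makes death without documented progression an event on the date of death. The note under the table settles overlaps: "PFS and associated outcome is determined by the earliest of the dates above, if more than 1 situation applies".

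Section 5.11.1 says of the primary Cox model: "All randomized patients, according to the ITT principle, will be included in the analysis of this endpoint". Section 5.3 sets the efficacy baseline as "the last non-missing measurement prior to randomization for demographic and efficacy analyses".

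**The concern.** Without a baseline scan, RECIST progression cannot be judged properly, which is a fair reason not to date a progression. It is no reason to set aside a dated death. Under Rule 1 the death of a randomized patient leaves an endpoint defined to include death from any cause. The patient stays in the ITT count but is censored on day 1 and adds essentially nothing to the log-rank test or the Cox model.

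The table also treats two similar gaps differently. A death in a patient with no postbaseline scan can be a PFS event; a death in a patient with no baseline scan cannot. At stake are a few events in the primary endpoint and the lack of any planned analysis showing whether they matter.

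**Working it through.** **Which rule governs.** Take a randomized patient with no baseline scan who dies.
- Rule 1 gives the randomization date, censored. Rule 6 gives the date of death, event.
- The ordered list in Section 5.3.1 puts the baseline condition first, and the note under the table takes the earliest date. Both lead to Rule 1, so Rule 6 cannot restore the death.
- For a patient with a baseline scan but no postbaseline scan, Rule 2 does not apply once the patient has died, and Rule 6 can count the death.

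**Whether a planned analysis restores the death.** The PFS analyses in Section 5.11.5 are:
- independent review, eCRF strata, unstratified, and stepwise Cox: these change the assessor or the model;
- per-protocol: a subset of ITT, which cannot add events;
- no censoring for new therapy (Rule 8), none for missed assessments (Rule 7), and both lifted;
- clinical progression counted as an event;
- loss to follow-up counted as progression (Rule 4).

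None is stated to change Rule 1. Beyond these the section allows only unspecified post-hoc analyses.

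**The plan's own figure.** Inputs from Section 5.1.2: 270 events, HR 0.71, 1-sided alpha 0.02499, 450 patients randomized 1:1. By Schoenfeld's formula, √270/2 × |ln 0.71| − 1.960 = 2.814 − 1.960 = 0.854, which gives power of 80.3%. The stated figure of at least 80% reproduces.

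**Effect on power.** The analysis is triggered by event count, so uncounted deaths are replaced by other events and power stays at 80.3%. If 5 deaths were instead lost from a fixed 270, power would be 79.6%.

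**Effect on the hazard ratio.** The SAP gives no number of affected patients. Assume that 1% of 450, or 4 to 5 patients, lack a baseline scan, and that k = 2 to 4 of them die before the cutoff, all in one arm. Take about 270/2 = 135 events and 450/2 = 225 patients per arm (equal split of events, a simplification).
- *Deaths near day 1.* Censoring removes the event and almost no exposure. The shift is about k/135: 2/135 = 1.5%, 4/135 = 3.0%.
- *Average exposure.* Censoring removes both. The shift is about k/135 − k/225: 1.48% − 0.89% = 0.6% for k = 2, and 2.96% − 1.78% = 1.2% for k = 4.

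A log-rank approximation for the near-day-1 case agrees in order of size. Each early death adds about 0.5 to observed minus expected, with variance 270/4 = 67.5 plus 0.25 per death. For k = 2 in the ramucirumab arm, (ln 0.71 × 67.5 + 1)/68 = −0.325, so the HR moves from 0.71 to 0.722, or 1.7%.

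**Chance that all fall in one arm.** If each death is equally likely in either arm, the probability is 2 × 0.5^k: 50% for k = 2 and 12.5% for k = 4.

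**The case against.** The strongest reply is that this is a deliberate choice. The text, the table and the note agree, and Rule 7 also censors some known deaths, so the SAP openly qualifies its definition of PFS. That stands: a reader might call Rule 1 a contradiction, but it is an explicit, consistently stated rule whose handling of deaths differs from Rule 2.

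Second, a reader might infer bias toward one arm. The documents do not support that. Under the Section 5.3 definition, baseline precedes randomization, so treatment cannot affect who falls under Rule 1, and any imbalance in lost deaths would be chance. Rules 7 and 8 depend on what happens after randomization, and those are the rules that Section 5.11.5 tests.

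Third, the case should be rare. Section 6 places randomization after screening is complete, and nothing shows that any patient lacked a baseline scan. One could imagine a scan taken after randomization but before first dose failing the baseline definition, but the SAP gives no sign that this occurs.

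Fourth, little is hidden. Section 5.11.1 summarizes reasons for censoring, Section 5.7 lists PFS and OS by patient, and the deaths count in OS. This limits the harm, but the deaths remain outside every planned PFS estimate.

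**Conclusion.** The point holds as a minor one. Known deaths in randomized patients without a baseline scan are excluded from primary PFS, and no prespecified analysis shows the result with them included. The cost is lost events and information, with no demonstrated bias.

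The effect is probably very small. The range is roughly 0.6% to 1.2% on the HR at average exposure, rising to about 1.5% to 3% only for deaths near day 1. It assumes 2 to 4 lost deaths, all in one arm, and the documents support neither assumption.

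A reader could go further and argue that the rule might decide the trial. With an observed HR of 0.78 (1-sided p about 0.021, against a critical HR of about 0.788), restoring two early deaths, both in the ramucirumab arm, would give p about 0.028. That is a constructed worst case. It needs a borderline result, very early deaths and a one-sided split, and nothing in the SAP makes that combination likely.

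**What to change.** Either change is enough:
- Add to Section 5.11.5 a PFS sensitivity analysis that counts death as an event on its date for patients with no baseline assessment. This leaves the primary analysis untouched.
- Or limit Rule 1, and the matching text in Section 5.3.1, to patients with no baseline tumor assessment and no death, in line with Rule 2.

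The wording should say whether Rule 7 applies to these deaths, since otherwise later ones could be censored back to randomization. It should also say that a progression recorded without a baseline does not date the event.

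The cost is a sentence or one more analysis, settled before unblinding, with no new data. The drawback is that within this small subset only patients who die are credited with follow-up, while survivors remain censored at randomization. Rule 2 already works that way.
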